9.7.2. Sample size determination

Approximately 3000 patients will be included with close to a 1:1 ratio between palbociclib + AI and AI alone cohorts. The median OS for AI alone is assumed to be 40 months. An improvement of 25% to a median OS of 50 months (corresponding to a hazard ratio of 0.80) would be considered clinically meaningful. Therefore, 750 OS events will be required to have at least 80% power to detect a hazard ratio of 0.80 using a two-sided log-rank test at a significance level of 0.05 based on the exponential distribution assumptions of OS for both cohorts.

9.7.3. Cohorts for Analysis

All effectiveness analyses will be based on the following 4 cohorts.

Cohort 1: Patients treated with palbociclib + an AI as the first line therapy in postmenopausal women or men with MBC

Cohort 2: Patients treated with an AI alone as the first-line therapy in postmenopausal women or men with MBC

Cohort 3: Pre or perimenopausal women treated with palbociclib + an AI as the first line therapy for MBC

Cohort 4: Pre or perimenopausal women treated with an AI alone as the firs-line therapy for MBC

9.7.4. Statistical Analysis

All analyses will be performed by using SAS® Version 9.1.4 or higher.

9.7.4.1. Inverse probability treatment weighting (IPTW)

Inverse probability treatment weighting will be used to balance baseline demographic and clinical characteristics between comparison cohorts (for instance, palbociclib + AI versus AI alone) in statistical analyses³². Variables to be used in the computation of propensity scores (PS) required to perform IPTW include key baseline demographics (e.g. age, race, practice type) and clinical characteristics (e.g. ECOG performance score, disease stage at initial diagnosis, visceral metastasis, number of disease sites, disease free interval, and comorbidities). In the event that IPTW method does not balance potential confounder variables, analysis by PS quintiles will be used.

9.7.4.2. Analyses of primary endpoint

The primary endpoint OS is defined as the time from the starting index date (01 February 2015) to the date of death. Patients who did not die within the follow up cut-off date are censored at data cutoff date.

A weighted log-rank test using IPTW (one-sided) will be used to compare OS time between palbociclib + an AI and an AI alone cohort at the analysis with the significance level at 0.05 (two-sided). OS time associated with each treatment arm will be summarized for Cohort 1 using the weighted Kaplan-Meier method and displayed graphically where appropriate. CIs for the 25th, 50th and 75th percentiles of the event-free time will be reported. OS rates at 12, 24, 36, 48, and 60 months will be estimated with corresponding 2-sided 95% CIs using the weighted Kaplan-Meier method. The weighted Cox Proportional hazards model will be fitted to compute the hazard ratio and the corresponding 95% CI.

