This study will compare real-world effectiveness outcomes for patients treated with palbociclib +AI versus AI alone as first line treatment for HR+/HER2- MBC in the Flatiron dataset initiating therapy between 03 February 2015 and March 2020. The primary endpoint will be overall survival (OS).

Primary Objective

 To compare overall survival (OS) of first line palbociclib + AI versus AI alone for postmenopausal women or men with HR+/HER2- MBC

Secondary objectives

- To compare real-world progression free survival (rwPFS) and real-world tumor response (rwTR) of first line palbociclib + AI versus AI alone for postmenopausal women or men with HR+/HER2- MBC
- To describe treatment patterns of palbociclib, including initial dose, dose adjustments, treatment duration, subsequent treatments, and time to chemotherapy

Study design:

The study is designed to evaluate the effectiveness of palbociclib + AI versus AI alone as first line treatment for HR+/HER2- MBC.

This is a retrospective observational cohort study utilizing data derived from the Flatiron Health Analytic Database to compare effectiveness outcomes in patients receiving palbociclib + AI versus AI alone as first line treatment for HR+/HER2- MBC. Study patients have HR+/HER2- MBC and have initiated palbociclib + AI or AI alone as the first line of anti-cancer treatment during the period of February 2015 through March 2020 in the US real-world clinical practice setting.

The date of the initiation of palbociclib + AI or AI alone as the first line of therapy in the metastatic setting between 03 February 2015 and March 31, 2020 is defined as the index date.

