8. RESEARCH QUESTION AND OBJECTIVES

This study aims to assess real-world effectiveness in HR+/HER2- MBC patients initiating palbociclib + AI or AI alone as first-line therapy during the period 01 February2015 through March 2020.

Primary Objective

• To compare overall survival (OS) of first line palbociclib + AI versus AI alone for postmenopausal women or men with HR+/HER2- MBC

Secondary objectives

- To compare real-world progression free survival (rwPFS) and real-world tumor response (rwTR) of first line palbociclib + AI versus AI alone for postmenopausal women or men with HR+/HER2- MBC
- To describe treatment patterns of Palbociclib, including initial dose, dose adjustment, treatment duration, subsequent treatments, and time to chemotherapy

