9. RESEARCH METHODS

9.1. Study design

The primary objective of the retrospective EHR database analysis is to compare effectiveness outcomes of palbociclib + AI versus AI alone as first line MBC treatment for HR+/HER2-MBC postmenopausal women or men.

The following table lists 7 key components of the study protocol.

D 4 10	D '.'
Protocol Component	Description
Eligibility criteria	All patients with HR+/HER2- MBC who were initiated with palbociclib + AI or AI alone as 1 st line therapy for their MBC during the period of February 2015 through March 2020 were registered in the Flatiron Health Analytic Database
Treatment regimen	Palbociclib + AI or AI alone as the first line MBC treatment
Study cohorts	Patients will be divided into either Palbociclib + AI or AI alone cohort according to their first line MBC treatment received
Follow-up period	From index date (i.e., starting date of the first line MBC treatment during the period of 03 February 2015 through March 2020) to death or study end (date of data cutoff, September 30, 2021), whichever occurred first
Primary outcome	Overall survival (OS)
Causal contrasts of interest	Intention-to-treat effect
Analysis plan	Intention-to-treat effect requires adjustments for baseline prognostic factors using IPTW approach. In addition, to address unmeasured confounding, sensitivity analyses will also be performed to determine the robustness of the estimated intention-to-treat effects.

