Time to 1st subsequent chemotherapy	Months from the start of palbociclib plus AI or AI alone to next line of anticancer therapy/chemotherapy, death form any cause, last visit, or end of study, whichever came first
Effectiveness outcomes	
Real-world PFS (rwPFS)	Real-world PFS is defined as the number of months from start of palbociclib + AI or AI alone to death from any cause or disease progression (based on clinical assessment or by radiographic

Protocol Amendment 1, 16 Feb 20	scan/tissue biopsy), whichever occurred first. Patients who did not die and did not have disease progression will be censored at the date of initiation of next line of therapy for patients with 2 or more lines of therapy or at the date of their last visit during the study period (February 2015- September 2020) for patients with only 1 line of therapy.
rwPFS2	rwPFS2 is defined as the number of months from start of palbociclib + AI or AI alone to disease progression (based on clinical assessment or by radiographic scan/tissue biopsy) on the 2 nd line of therapy or death from any cause, whichever occurred first. Patients who did not die and did not have disease progression on the 2nd line of therapy will be censored at the date of initiation of 3 rd line of therapy for patients with 3 or more lines of therapy or at the date of their last visit during the study period (February 2015- September 2020) for patients with only 1 or 2 lines of therapy ²⁹ .
Overall survival (OS)	Overall survival (OS) was defined as the number of months from start of palbociclib + AI or AI alone to death. Patients who did not die, will be censored at the end of study date. Date of death. In most Flatiron deliverables, death data is delivered with a month granularity. Date of death is a consensus variable across the three data sources (EHR, SSDI and obituary data). Flatiron generates the variable according to the following rules and hierarchy (preference is based on comparative analyses with the National Death Index as the gold standard): Use abstracted dates over structured dates when the abstracted date granularity is at the day level. Use the following rules when there are multiple structured dates of death: If all three dates are in agreement, that date of death is selected If any two dates are in agreement, that date of death is selected If none of the dates are in agreement, then the rank order to which the date of death is selected is: SSDI→Obituary data→EHR

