9.7.4.3. Analyses of secondary CC

Real-world progression-free survival (rwPFS) is defined as the time from index date to the date of the first documentation of a rwPD or death due to any cause, whichever occurs first. Patients last known to be alive and progression-free within the follow up cut-off date are censored at the date of the last clinic note. rwPFS2 is defined as the time from the index date to the date of the first documentation of a rwPD or death due to any cause after starting 2nd line of therapy, whichever occurs first.

rwPFS and rwPFS2 will be summarized using the weighted Kaplan-Meier method and displayed graphically where appropriate. The median rwPFS/PFS2 time will be estimated and corresponding 2-sided 95% CI for the median using the Brookmeyer-Crowley method.

rwPFS rates at 6, 12, 18, 24, 30, and 36 months will be estimated with corresponding 2-sided 95% CIs using the weighted Kaplan-Meier method. The weighted Cox Proportional hazards model will be fitted to compute the hazard ratio and the corresponding 95% CI.

Real-world tumor responses (rwTR) are assessed based on treating clinician's assessment of radiological evidence for change in burden of disease over the course of treatment after 30 days of index treatment initiation.

- Complete response: complete resolution of all visible disease.
- Partial response: partial reduction in size of visible disease in some or all areas without any areas of increase in visible disease.
- Stable disease: no change in overall size of visible disease; also included cases where some lesions increased in size and some lesions decreased in size
- Progressive disease: an increase in visible disease and/or presence of any new lesions; included cases where the clinician indicated progressive disease.

Real-world tumor response rate (rwTR) is defined as the proportion of patients with a real-world complete response (rwCR) or real-world partial response (rwPR). Patients who have inadequate data for tumor assessment (e.g. no baseline assessment or no post-baseline follow-up assessments), who receive anticancer medication other than the study medication prior to reaching a rwCR or rwPR, or who die, progress, or drop out for any reason prior to reaching a rwCR or rwPR will be counted as non-responders in the rwTR analysis.

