9.8. Quality control

This is a retrospective study, therefore issues of quality control at study sites, e.g. data clarification queries, do not apply. Analyses are programmed according the specifications in the protocol's SAP and all code and other technical artifacts are documented and stored following established programming practices on Pfizer servers and in Pfizer's Global Document Management System. Quality control (QC) will follow the Flatiron's standard procedure for quality control and assurance as described in Flatiron Health Analytic Database Parent Protocol. QC for structured and unstructured data is conducted prior to delivery of each dataset. For each data model, Flatiron generates and continually maintains a set of quality standards and versioned business rules. These QC standards cover themes such as demographics, biomarkers, treatment, therapy shares, treatment length/dosage, lines of therapy, real-world recurrence, and real-world progression free survival. They have a team of

900 expert nurse and physician abstractors that co-create and version rules, and also to create QC that includes both medical considerations (e.g. what are expected based on the literature and clinical practice) and data considerations (e.g. stability from prior months). Missingness of death data is a major confounding factor for many real-world oncology analyses. For survival data, Flatiron Health utilizes 4 resources, including the National Death Index, US Social Security Death Index, obituaries, and commercial death data published from a vendor to identify when patients have died (https://onlinelibrary.wiley.com/doi/full/10.1111/1475-6773.12872). In a study of advanced non-small cell lung cancer patients, sensitivity increased from 66% from Flatiron's EHR-based registry alone to over 91% from the composite of the 4 sources.

QC will be performed for the results of the study, including reviewing and double checking for correct data, consistency, spelling, grammar, and structure. It is also reviewed to ensure that it conforms to Flatiron's data dictionary, has internal consistency (e.g. that date of diagnosis occurs after date of birth) and meets the study objectives. The final review of the findings and content will be conducted in a summary presentation.

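### Protocol 9.7.4.2 starts the OS clock on one calendar date and Protocol 9.1 gives a data cutoff a year later than the rest of the plan; both are drafting errors to correct (minor)

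*Protocol*

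**What the plan says.** **Time origin.** The primary-analysis section, Protocol 9.7.4.2, reads: "The primary endpoint OS is defined as the time from the starting index date (01 February 2015) to the date of death". It continues: "Patients who did not die within the follow up cut-off date are censored at data cutoff date".

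The rest of the plan uses a patient-level origin:
- Abstract: first-line initiation "in the metastatic setting between 03 February 2015 and March 31, 2020 is defined as the index date".
- Protocol 9.1, follow-up period: "From index date (i.e., starting date of the first line MBC treatment during the period of 03 February 2015 through March 2020".
- Protocol 9.3, repeated in SAP 5.1: "Overall survival (OS) was defined as the number of months from start of palbociclib + AI or AI alone to death".
- Protocol 9.7.4.3, the section straight after: "Real-world progression-free survival (rwPFS) is defined as the time from index date to the date of the first documentation of a rwPD", with no calendar date attached.

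The day 01 February 2015 appears in one other place, Protocol 8, as the start of a period: "as first-line therapy during the period 01 February2015 through March 2020".

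**Cutoff.** The follow-up row of the Protocol 9.1 table ends the study at a data cutoff of 30 September 2021. Inclusion criterion 5 (Protocol 9.2.1 and SAP 4.1) names 30 September 2020. The Abstract, Protocol 9.3, SAP 2.1 and SAP 5.1 end the study period in September 2020.

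**Which document governs.** Protocol 9.8 says: "Analyses are programmed according the specifications in the protocol's SAP". Protocol 9.7 lets the SAP modify the protocol, but requires major changes to primary endpoint definitions to appear in a protocol amendment as well.

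**The concern.** A survival time needs an origin that belongs to the patient. Measured from one shared calendar day, every patient would carry an event-free stretch before treatment, and its length would depend only on when that patient happened to start. OS medians and the planned 12- to 60-month rates would then not describe survival on first-line therapy.

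The cutoff fixes how long patients are observed and how many deaths are counted, so it should have one value throughout.

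Both statements are in operative text: the protocol's definition of its primary endpoint and its table of key design components. A report that correctly follows the SAP would not match either place.

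**Working it through.** **1. Reproduce the plan's own figure.** Criterion 5 asks for at least 6 months of potential follow-up. The last index date is 31 March 2020 (Abstract). To 30 September 2020 is 183 days; 183 / 30.4375 = 6.0 months. The stated minimum agrees with the 2020 cutoff. To 30 September 2021 is 548 days, or 18.0 months. That also meets a 6-month minimum, so the length of the minimum does not by itself exclude 2021. The date written into the criterion does conflict with it.

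**2. Milestones (Protocol 6).** Curation was planned to finish on 30 June 2021 and the primary-objective analysis to start on 01 September 2021. A cutoff of 30 September 2021 falls after both.

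**3. Literal effect of the fixed origin.** Pre-treatment time added = index date minus 01 February 2015.
- Earliest index date, 03 February 2015: 2 days.
- Latest index date, 31 March 2020: 1,885 days / 30.4375 = 61.9 months.

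**4. Effect of the cutoff year on potential follow-up.**

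| Cutoff | Last patient in | First patient in (03 Feb 2015) |
|---|---|---|
| 30 Sep 2020 | 183 days = 6.0 months | 2,066 days = 67.9 months |
| 30 Sep 2021 | 548 days = 18.0 months | 2,431 days = 79.9 months |

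**5. Effect of the cutoff year on deaths.** From Protocol 9.7.2: about 3,000 patients at close to 1:1 (taken as 1,500 per arm) and exponential OS with medians of 40 and 50 months. Assumptions not in the documents: uniform entry, no loss to follow-up and complete death capture. With λ = ln 2 / median, and potential follow-up running from a to b months,

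expected deaths per arm = 1,500 × [1 − (e^(−λa) − e^(−λb)) / (λ(b − a))].

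| Cutoff | a, b | AI alone | Palbociclib + AI | Total |
|---|---|---|---|---|
| 2020 | 6, 67.9 | 671 | 573 | 1,244 |
| 2021 | 18, 79.9 | 827 | 715 | 1,542 |

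1,542 / 1,244 = 1.24, so about 24% more deaths. The totals are illustrative: 1,244 is 66% above the protocol's 750. A death-capture fraction common to both cutoffs scales both totals and leaves the ratio at 1.24.

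**6. Event requirement.** The 750 events in Protocol 9.7.2 rest on the hazard ratio, alpha and power. Neither date enters, so that requirement is unaffected.

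**The case against.** The strongest reply is that nothing will go wrong. Programming follows the SAP, and SAP 2.1, 4.1 and 5.1 have the right origin and cutoff. The protocol is also right in most places, and the parenthesis in 9.7.4.2 is most naturally the period start from section 8 put in the wrong spot. An SAP-based report would match the protocol's operational definition in 9.3. Most of this stands, and it is why the point is minor. It does not make the two passages correct. The start of a window is not a time origin, 03 February is the start used elsewhere for the index date, and 9.7 expects the protocol itself to carry the primary endpoint definition.

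A reader might infer that the primary hazard ratio is at risk. In simulation (1,500 per arm, 2020 cutoff) with the same uniform entry in both arms, the fixed origin moves a true 0.80 only to about 0.81. A large distortion needs entry times that differ by arm. If palbociclib starts averaged about 37 months into the window against 25 for AI alone, a true hazard ratio of 1.00 would read about 0.66. That pattern is an assumption: the documents give no entry distribution by arm, and the SAP does not use this origin.

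A reader might also tune the death calculation to 750 and obtain a larger effect of the cutoff year. One route needs about 60% death capture (750 / 1,244), against the 85–90% sensitivity in Protocol 9.4.2. The other needs entry so late that observed median follow-up is about 13 months. The prior study had 24.2 months, and Protocol 7 expects longer here. Neither is supported.

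**Conclusion.** Wrong as written, minor: a document-consistency correction. Protocol 9.7.4.2 contradicts the patient-level OS origin used elsewhere in both documents, and the 9.1 cutoff contradicts every other statement of it and the primary-analysis milestone.

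The date arithmetic (2 days to 61.9 months of added time; follow-up of 6.0–67.9 against 18.0–79.9 months) rests on the documents alone. The 24% rise in deaths rests on the uniform-entry and exponential assumptions. All of this describes a literal reading; with the SAP followed, no wrong analysis is expected.

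One neighbouring difference should not be folded into this correction. The Abstract censors OS at last follow-up or data cutoff, whereas Protocol 9.3, 9.7.4.2 and SAP 5.1 use end of study or data cutoff. A reader might take that as another slip to tidy by deleting words. It is a substantive choice: patients and practices leave the database (Protocol 7), and 85–90% sensitivity means 10–15% of deaths may be missed. It needs to be reconciled on its merits.

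**What to change.** - **Protocol 9.7.4.2:** delete the parenthetical 01 February 2015 and define OS from each patient's own index date, the start of first-line treatment.
- **Protocol 9.1:** change the cutoff to 30 September 2020, after confirming it against the delivered dataset.
- **Optional, Protocol 8:** align the period start with 03 February 2015.

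The cost is two short protocol edits, a third if section 8 is aligned, and one check of the dataset's cutoff. This correction needs no SAP change, new data or extra analysis.

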9.7.4.3. Analyses of secondary CC

Real-world progression-free survival (rwPFS) is defined as the time from index date to the date of the first documentation of a rwPD or death due to any cause, whichever occurs first. Patients last known to be alive and progression-free within the follow up cut-off date are censored at the date of the last clinic note. rwPFS2 is defined as the time from the index date to the date of the first documentation of a rwPD or death due to any cause after starting 2nd line of therapy, whichever occurs first.

rwPFS and rwPFS2 will be summarized using the weighted Kaplan-Meier method and displayed graphically where appropriate. The median rwPFS/PFS2 time will be estimated and corresponding 2-sided 95% CI for the median using the Brookmeyer-Crowley method.

rwPFS rates at 6, 12, 18, 24, 30, and 36 months will be estimated with corresponding 2-sided 95% CIs using the weighted Kaplan-Meier method. The weighted Cox Proportional hazards model will be fitted to compute the hazard ratio and the corresponding 95% CI.

Real-world tumor responses (rwTR) are assessed based on treating clinician's assessment of radiological evidence for change in burden of disease over the course of treatment after 30 days of index treatment initiation.

- Complete response: complete resolution of all visible disease.
- Partial response: partial reduction in size of visible disease in some or all areas without any areas of increase in visible disease.
- Stable disease: no change in overall size of visible disease; also included cases where some lesions increased in size and some lesions decreased in size
- Progressive disease: an increase in visible disease and/or presence of any new lesions; included cases where the clinician indicated progressive disease.

Real-world tumor response rate (rwTR) is defined as the proportion of patients with a real-world complete response (rwCR) or real-world partial response (rwPR). Patients who have inadequate data for tumor assessment (e.g. no baseline assessment or no post-baseline follow-up assessments), who receive anticancer medication other than the study medication prior to reaching a rwCR or rwPR, or who die, progress, or drop out for any reason prior to reaching a rwCR or rwPR will be counted as non-responders in the rwTR analysis.

